6.3.2 Vital signs

Vital sign assessment consists of height (first visit), pulse, blood pressure, respiration rate, temperature and weight.

6.3.3 Physical examination

Physical examination will be performed which must comprise a total body examination.

Significant findings made after the start of study drug which meet the definition of an Adverse Event must be recorded.

6.3.4 Laboratory evaluations

Laboratory evaluation should be done at screening (within 28 days of cycle 1, day 1), and on day 1 of each treatment cycle. Results must be reviewed prior to administering Elotuzumab. More frequent examinations may be performed if medically indicated; results should be recorded.

Hematology

Hematology must include hemoglobin, hematocrit, platelets, total white blood cell count (WBC) and differential.

Blood chemistry

Biochemistry includes the following parameters: BUN, creatinine, sodium, potassium, chloride, CO_2 (HCO_3), glucose, calcium, albumin, total protein, total bilirubin, alkaline phosphatase, AST/SGOT, ALT/SGPT. If total bilirubin is greater than the upper limit of normal, direct and indirect bilirubin should be performed.

Serum pregnancy test

All females of childbearing potential should complete a serum pregnancy test within 7 days prior to the administration of Elotuzumab and lenalidomide on day 1 of cycle 1. The pregnancy test should be repeated in week 1 of every cycle (except for cycle 1). Postmenopausal women must have been amenorrheic for ≥ 12 months in order to be considered "of non-childbearing potential".

Performance status

Performance status will be assessed by ECOG performance status scale.

6.4 Disease assessments

Disease assessments will be performed at Screening (within 28 days before dosing on Cycle 1 Day 1) and at Day 1 of each treatment cycle.

Disease assessments at Screening (within 28 days before dosing on Cycle 1 Day 1) include the following:

- Serum protein electrophoresis (SPEP), urine protein electrophoresis (UPEP; 24-hour assessment, no substitute method is acceptable), and immunofixation
- SFLC
- Quantitative immunoglobulins
- Skeletal bone survey

Disease assessments at Day 1 of Cycle 2, and each cycle thereafter, and at the EOT include the following:

- Serum protein electrophoresis (SPEP), urine protein electrophoresis (UPEP; 24-hour assessment, no substitute method is acceptable. For patients with urine M spike of less than 200 mg/24 hours at screening, 24 hour urine collection with UPEP will be done every other cycle), and immunofixation
- SFLC
- Quantitative immunoglobulins

The following disease assessments will be performed post baseline as noted below:

· Bone marrow sample – On cycle 2 day 1 for lab correlative studies, then only required to confirm a complete response (CR) and at time of clinical relapse

Serum protein electrophoresis, UPEP, SFLC, and quantitative immunoglobulin analyses will be performed at the local laboratory.

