- Elotuzumab 10 mg/kg IV weekly (days 1, 8, 15 and 22) for 2 cycles, then 20 mg/kg every 4 weeks
- Lenalidomide 10 mg PO daily days 1-21 out of a 28-day schedule

Response assessment:

The Consensus on Uniform Reporting of Response will be used to evaluate response.⁴ Myeloma patients enrolled in this clinical study will be assessed for disease response after every cycle. Time to disease progression will be defined as the time from the day first Elotuzumab treatment to the time of myeloma progression.

4 Study population

Patients with multiple myeloma who demonstrate evidence of serologic relapse/progression while on lenalidomide maintenance given as part of **first** line therapy (including upfront high-dose chemotherapy followed by autologous hematopoietic cell transplantation (HCT)) without symptomatic relapse/progression. Lenalidomide maintenance is defined as **single agent** lenalidomide therapy of any doses up to 15 mg PO daily for up to 28 days (28-day cycle). Relapse/progression is defined as increase of 25% from the lowest response value (for either serum or urine M-spikes), absolute increase in serum M-spike ≥ 0.5 g/dL, absolute increase in urine M-spike ≥ 200 mg/24hour, or the difference between involved and uninvolved free light chain (FLC) levels of absolute increase with > 10 mg/dl (only for those without measurable serum and urine M-spikes) There will be 30 subjects in each cohort for total accrual of 60 subjects.

Patients must have baseline evaluations performed prior to the first dose of study drug and must meet all inclusion and exclusion criteria. Results of all baseline evaluations, which assure that all inclusion and exclusion criteria have been satisfied, must be reviewed by the Principal Investigator or Co-investigators prior to enrollment of that patient. In addition, the patient must be thoroughly informed about all aspects of the study, including the study visit schedule and required evaluations and all regulatory requirements for informed consent. The written informed consent must be obtained from the patient prior to enrollment. The following criteria apply to all patients enrolled onto the study unless otherwise specified.

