5.2 Treatment cycle and duration

Treatment cycles will have a duration of 28 days and subjects will receive Elotuzumab on days 1,8,15, and 22 of cycles 1-2 and on day 1 on cycle 3 and beyond, in combination with lenalidomide at either 25 mg (cohort A) or 10 mg (cohort B) on days 1-21. All cycles will start 28 days (\pm 3) after the start of the prior cycle.

Subjects will continue therapy until one of the following:

1. Disease progression
2. Withdrawal from the study for any reason
3. Death

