5.8 Dose modifications for lenalidomide-related toxicity

Dose reduction levels for lenalidomide for toxicity management of individual subjects are provided in Table 6:

Table 6 Dose Decrements for Lenalidomide

Nominal Dose (mg)	Reduced Lenalidomide Doses (mg)		
	Dose -1	Dose -2	Dose -3
25	15	10	5
10	5	Discontinue	—

Treatment guidelines for specific hematologic toxicities and nonhematologic toxicities are outlined below. In addition to dose reductions, administration of lenalidomide may be held temporarily in the event of a treatment related toxicity at the investigator's discretion.

If the lenalidomide dose is reduced during a given cycle, the reduced dose level will be continued for the next cycle. If the reduced dose level is tolerated for a complete cycle, the subject may, at the investigator's discretion, resume the dose level prior to the reduction at the start of the subsequent cycle.

Lenalidomide can be discontinued in the event of a treatment-related toxicity that, in the opinion of the investigator, warrants discontinuation. The subject will be considered still on protocol treatment as long as Elotuzumab is being administered.

5.8.1 When platelets	5.8.2 Lenalidomide
5.8.3 Fall to $< 30 \times 10^9 / \text{L}$	5.8.4 Hold dose, hold anticoagulation follow CBC weekly, resume at 1 dose decrement after platelets returned to $> 30 \times 10^9 / \text{L}$

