5.9.1.1 Follow-up for toxicities

Patients whose treatment is interrupted or permanently discontinued due to an adverse event or abnormal laboratory value must be followed until resolution or stabilization of the event, whichever comes first.

If a patient requires a dose delay of > 21 days from the intended day of the next scheduled dose, then the patient must be discontinued from the study. If however the patient was clearly benefiting from therapy, the patient may be able to continue treatment with either a 5 mg or 10 mg dose reduction at the Investigator discretion, after resolution of the adverse event. All patients will be followed for adverse events and serious adverse events for at least 4 weeks following the last dose of study treatment.

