5.11 Treatment compliance

Records of study medication used, dosages administered, and intervals between visits will be recorded during the study.

6 Visit schedule and assessments**6.1 Visit schedule****Table 6-1****Evaluation and visit schedule**

Assessment	Screening 0-28 days	Day 1 Cycles 1- 2	Day 8	Day 15	Day 22	Day 1 Cycle 3 - beyond	End of Study
Assessment	Screening 0-28 days	Day 1 Cycle 1&2 +/- 3 days	Day 8	Day 15	Day 22	Day 1 C3- beyond +/- 3 days	End Of Study
Informed Consent	X						
Inclusion/exclusion criteria	X						
Vital signs, Physical examination and ECOG Performance Score ⁶	X	X				X	X
Concomitant medications ⁶	X	X				X	X
CBC + diff ⁶	X	X	X	X	X	X	X
CMP ⁶ ,Pregnancy Test ⁶	X	X	X	X	X	X	X
SPEP/UPEP ⁸ /immunofixation	X	X				X	X
Serum free light chains	X	X				X	X
Quantitative immunoglobulins	X	X				X	X
Skeletal survey ³	X					X ³	X ³
Bone marrow asp and bx with Cytogenetics, MM Fish Panel Lab correlative studies ¹		X ¹	X ¹				X ¹
MRD Testing	X ²						
Response Assessment	n/a						X
Study Drug Diaries	n/a	X				X ⁵	

Adverse Events ⁷	n/a	X	X	X		X	X
-----------------------------	-----	---	---	---	--	---	---

1. Bone marrow aspirate and biopsy will be done at screening and on cycle 2 day 1, and to confirm CR after 4 cycles, 8 cycles and as indicated and at time of PD for lab correlative studies as outlined in page 26. In parallel a peripheral blood sample will be collected for lab correlative studies at same time points and on day 1 of each cycle. Bone marrow aspirates (30mL volume) for correlative studies will be collected at baseline, Cycle 2 day 1, and thereafter for confirmation of CR, and at time of disease progression to analyze marrow-infiltrating immune populations by MPFC. In parallel, PBMCs, isolated from 20-30mL freshly drawn sample, will be analyzed similarly at 4-week intervals corresponding to Day 1 of each cycle as well as at time of progression.
2. MRD testing will be performed at screening, by flow cytometry and NSG on patients and as indicated on patients in hematologic complete remission. An aliquot of serum will be stored for those patients with IgG MM who achieved VGPR to evaluate extent of interference by the antibody therapy.
3. Bone survey will be done at screening and once yearly or when clinically indicated. May be substituted by PET scan or MRI as clinically indicated
4. Response assessment will be done every 2 cycles.
5. Study drug diaries will be collected after each cycle

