6.2 Efficacy assessments

Response will be determined by the investigator based on the disease assessments described above and the IMWG-URC (see definitions in [Appendix B](#)). Myeloma response will be assessed at the beginning of each cycle.

The following confirmatory assessments are required for all response categories (stringent complete response [sCR], CR, VGPR, and PR) and progressive disease:

- All laboratory-based progressive disease and all responses require 2 consecutive assessments made at any time before initiation of any new therapy. Confirmatory lab samples should be separated by at least 1 calendar day
- Progressive disease by nonlaboratory-based assessment (i.e.; plasmacytoma or skeletal lesion) does not require confirmatory report
- All response categories also require no evidence of progression including new bone lesions if radiographic studies were performed
- Confirmation of CR or sCR requires bone marrow biopsy or aspirate slides (a confirmatory bone marrow sample is not required)
- Extramedullary plasmacytoma evaluation (if present at baseline)

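### Disease assessments follow cycle Day 1, and nothing says whether a dose hold moves Day 1, so detection of progression can be postponed; the effect on PFS is small and in one direction

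*Combined protocol and SAP*

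**What the plan says.** **Assessment timing.** Section 6.4 places serum and urine electrophoresis, immunofixation, free light chains and immunoglobulins at screening "and at Day 1 of each treatment cycle". Section 6.2 agrees: "Myeloma response will be assessed at the beginning of each cycle". Table 6-1 has the same Day 1 columns. For patients whose screening urine M spike is below 200 mg/24 h, 6.4 says that "24 hour urine collection with UPEP will be done every other cycle". Section 3 says that patients "will be assessed for disease response after every cycle", while footnote 4 of Table 6-1 says "Response assessment will be done every 2 cycles". That last conflict is a separate matter; the present point arises even with assessment every cycle.

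**Cycle timing.** Section 5.2 states "All cycles will start 28 days" (±3) after the start of the prior cycle. Table 6-1 repeats the ±3 days for Day 1. Section 6.5 describes the blood sampling for correlative studies as four-weekly, matching Day 1.

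**Holds and delays.** Section 5.8 says that "administration of lenalidomide may be held temporarily in the event of a treatment related toxicity at the investigator's discretion". Section 5.9.1.1 sets the limit for leaving the study: "If a patient requires a dose delay of > 21 days from the intended day of the next scheduled dose", with an exception, without an upper limit, for a patient clearly benefiting.

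**Endpoint.** PFS is the primary endpoint, counted from randomization (7.1), and section 7 plans each cohort against a fixed null median of 7 months. The comparison of cohorts is exploratory in section 7 and listed as a secondary objective in 2.2.

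**The concern.** Much of the progression in this population will be found by scheduled laboratory tests, so the date of the next test largely sets the PFS date. If a dose delay moves Day 1, no disease assessment falls due until the delayed Day 1. At the 21-day limit that is 28 + 21 = 49 days after the last one, and more under the exception. If the site keeps the 28-day grid and withholds only the drug, the assessment stays on time. Two sites could each point to a section of the protocol and record different progression dates for the same patient.

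A slipped assessment can only move detection later, never earlier. Each cohort is read against a fixed 7-month median with no concurrent control, so nothing offsets the shift. If delays also differed between the lenalidomide doses, the exploratory cohort comparison would be touched as well.

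**Working it through.** **1. The plan's own figure.** Inputs from section 7: null median 7 months, alternative 12 months, 24 months accrual (A), 12 months follow-up (F), one-sided alpha 0.05, 30 patients per cohort. With exponential PFS and uniform accrual, the probability of an event is 1 − [exp(−λF) − exp(−λ(A+F))]/(λA), with λ = ln 2/median.
- Null: 0.884 × 30 = 26.5 events.
- Alternative: 0.729 × 30 = 21.9 events.
- Power = Φ((ln(12/7) − 1.645/√26.5) × √21.9) = Φ((0.539 − 0.320) × 4.68) ≈ 84.8%.

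This reproduces the stated 85%. The planning model treats progression times as observed exactly.

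**2. Mean detection lag.** If progression is read at the next assessment and the interval between assessments is L days, the mean lag is E[L²]/(2E[L]). With L = 28 always, it is 14 days. Suppose a share p of intervals is lengthened by D days. The documents give no delay rate, so p and D are assumptions. Months are taken as 30.44 days.

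| p | D (days) | E[L] | E[L²] | Mean lag (days) | Extra (days) | Extra (months) |
|---|---|---|---|---|---|---|
| 20% | 14 | 30.8 | 980 | 15.9 | 1.9 | 0.06 |
| 20% | 21 | 32.2 | 1107.4 | 17.2 | 3.2 | 0.10 |
| 25% | 21 | 33.25 | 1188.25 | 17.9 | 3.9 | 0.13 |
| 50% | 21 | 38.5 | 1592.5 | 20.7 | 6.7 | 0.22 |
| 100% | 21 | 49 | 2401 | 24.5 | 10.5 | 0.34 |

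For comparison, the planned difference is 12 − 7 = 5 months.

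**3. Error rate against 7 months.** Section 7.1 names Kaplan-Meier and a Brookmeyer-Crowley interval but no test. A one-sided log-hazard test was therefore assumed, with 30 patients, the accrual and follow-up above, and exponential PFS. Simulated rejection rates (Monte Carlo error about 0.2 to 0.3 points):

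| Observation of progression | True median 7 months | True median 12 months |
|---|---|---|
| Continuous | 3.9% | 82.3% |
| Every 28 days, no delays | 6.1% | 87.1% |
| 20% of cycles delayed 21 days | 6.6% | 88.0% |
| 50% of cycles delayed 21 days | 7.8% | 88.9% |

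The 28-day interval alone adds 6.1 − 3.9 = 2.2 points. Delays add 0.5 points (20% of cycles) or 1.7 points (50%).

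**4. Cohort comparison.** Suppose one cohort has 21-day delays, the other has none, and true PFS is identical. The apparent hazard ratio is then about 0.99 with 20% of cycles delayed and 0.97 to 0.98 with 50%.

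**The case against.** The best reply is that the plain text already fixes the grid. Section 5.2 lets Day 1 move by only 3 days and Table 6-1 repeats that window. The hold rules in 5.8 concern lenalidomide alone, and a patient stays on protocol treatment while elotuzumab continues. Section 5.7 modifies elotuzumab only for infusion reactions. Section 5.9.1.1 speaks of a dose delay, not a cycle delay. On this reading a lenalidomide hold leaves Day 1, and the assessment, where they were.

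That reading is reasonable, and it defeats the stronger inference that any toxicity delay necessarily postpones detection of progression. It does not close the gap: no section states that Day 1 stays put during a hold, and none keeps the tests on their planned date if it moves.

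A reader might also infer that the 25 mg cohort gains, because more holds might be expected there. No section gives a delay rate by cohort, so this is an assumption. Even if true, a hazard ratio of 0.97 to 0.99 could not be told from 1 with 30 patients per cohort.

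Two further points stand. Not every PFS event waits for a Day 1 test: deaths count when they occur, and plasmacytoma or skeletal progression needs no laboratory confirmation (6.2). And the 28-day interval itself accounts for much of the excess over 3.9%; calendar scheduling does not remove that part.

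**Conclusion.** The point holds as a gap in wording with a small statistical consequence. Wherever Day 1 slips, detection can be postponed and PFS lengthened; where Day 1 follows 5.2, there is no effect. The mean shift is 0.06 to 0.22 months in the partial-delay scenarios and 0.34 months if every cycle slips 21 days. Type I error against 7 months rises from 6.1% to between 6.6% and 7.8% when 20% to 50% of cycles are delayed 21 days. These figures assume exponential PFS, the stated delay patterns and a log-hazard test that the plan does not name. The documents do not support a claim that one cohort is favoured or that the trial's conclusion is at risk. The sample size is unaffected. Severity is low, but the direction is always the same and the remedy is cheap.

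**What to change.** In 6.4, 6.2 and Table 6-1, schedule all disease assessments by calendar time from cycle 1 day 1, whether or not dosing is held or a cycle start is delayed:
- serum tests every 28 (±3) days;
- 24-hour urine every 28 days, or every 56 days for patients with a screening urine M spike below 200 mg/24 h, which keeps the present frequency.

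Reconcile 5.2 and 5.9.1.1 on whether a hold shifts the cycle start. Which dosing rule applies is for the sponsor to decide; the assessment schedule should not depend on it.

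The cost is a wording change and an occasional extra draw or urine collection during a hold. The weekly CBC in 5.8 covers only platelet and ANC holds, so other holds may need a separate visit for blood. With the change, the mean lag returns to 14 days for tests on the 28-day schedule, whatever the delay rate in either cohort.

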6.5 MRD Testing and Lab correlatives (see study calendar)

Analysis of MRD status will be performed on all subjects by 2 methods:

1. Flow cytometry (FC) of cell surface markers and
2. Next Generation Sequencing (NGS) of DNA and/or RNA from the Ig locus.

The MRD analysis by FC will be performed on bone marrow aspirate samples collected at 2 time points: At screening and/or upon achieving a hematologic CR.

3. Identify phenotypic characteristics of the immune infiltrate that predict therapeutic efficacy of Elotuzumab and correlate with survival outcomes in MM care.

Predictive modeling of therapeutic efficacy in an era of immunotherapy must necessarily include parameters derived from immunologic aspects of the tumor microenvironment. The anti-myeloma immune response evolves in conjunction with the progression of disease²⁵⁻²⁸ while simple, distinctive patterns identified in the infiltrating immune population can hold prognostic relevance^{29,30}. Similarly, characterization of distinct phenotypic changes in peripheral blood lymphocytes (PBL) in high-risk smoldering MM patients exposed a pattern indicative of T cell dysfunction that was reversed with exposure to lenalidomide²⁸. In-depth characterization of lymphocytic and myeloid populations infiltrating the marrow of MM patients, monitoring changes in recruitment, phenotype and function of critical effector/regulatory populations, should identify critical queues that will inform clinical decisions to guide optimization of delivery of Elotuzumab in terms of timing and sequencing with ideal therapeutic partners such as IMiDs and checkpoint inhibitors. Furthermore, this signature should be detectable in circulating PBL using enhanced multiparameter flow cytometry (MPFC).

Table 1. MPFC Lymphocyte Analysis Parameters

CD3, CD4, CD8, CD56, Viability			
CD25 (IL-2R α) CD27 CD45RA CD194 (CCR4) CD195 (CCR5) CD197 (CCR7) CD95 (Fas) CD127 (IL-7R α) CD94 (NKG2D)	CD25 (IL-2R α) CD45RA CD194 (CCR4) IFN- γ IL-4 IL-17A FoxP3	CD152 (CTLA-4) CD279 (PD-1) CD223 (Lag-3) CD366 (Tim-3) CD244 (2B4) CD272 (BTLA) CD226 (DNAM-1) TIGIT	Proliferation (CTV) IFN- γ TNF- α Granzyme B
Maturation	Lymphocyte Subset	Exhaustion	Stimulation

populations, as well as NK and NKT cells), and (c) capacity, measured in terms of proliferative capacity and effector

We have developed an approach to define these immunologic populations in much greater detail using MPFC. Leukocytes will be isolated from bone marrow aspirates by Ficoll-Hypaque gradient centrifugation after prior extraction of MM cells by CD138 positive magnetic bead selection. In parallel, leukocytes will be isolated in similar fashion from peripheral blood samples from each patient. After adequate viability is determined (>85% viable by trypan blue exclusion), leukocyte cell fractions from each patient sample, will be prepared according to three defined analysis panels (see **Table 1**) to characterize (a) maturation state, (b) subset composition (e.g. T_H1, T_H2, T_H17, T_{REG}, and CD8 $^{+}$ counterpart exhaustion status. In addition, lymphocyte stimulatory capacity and effector cytokine production (i.e. IFN- γ TNF- α and

Granzyme B) will be assessed as a benchmark of immune function. In brief, CD3⁺ T cells will be isolated from the leukocyte fraction of each sample by magnetic bead selection

(Miltenyi Biotech) to achieve approximately

Table 2. Myeloid Characterization by MPFC.

Myeloid Panel	
CD11b	CD38
CD13	CD71
CD14	CD45
CD15	CD64
CD16	CD80
CD33	CD163
CD34	CD124
CD117	Statistical Methods
HLA-DR	

7

99% of final cell stain and the preparation for MPFC analysis. Comparative analysis of disease in the cell myeloid compartment will be monitored using a 14-parameter panel designed to detect dendritic cell, myeloid suppressor cell, and macrophage populations, as detailed in Table 2. Immunophenotypic profiles will be discerned from sequential analysis of the individual patient samples at defined intervals. Bone marrow aspirates (30mL volume) will be collected at baseline, Cycle 2 day 1, and thereafter for confirmation of CR, and at time of disease progression to analyze marrow-infiltrating immune populations by MPFC. In parallel, PBMCs, isolated from 20-30mL freshly drawn sample, will be analyzed similarly at 4-week intervals corresponding to Day 1 of each cycle as well as at time of progression.

Phase II study

